8.2 Continuous Monitoring for Toxicity

Sequential boundaries will be used to monitor unacceptable toxicity rate in the trial. An unacceptable toxicity is defined as any drug-related grade 3 non-hematologic toxicity (exceptions include infusion reactions, rash, fever, infection, nausea, fatigue and anorexia) persisting for >7 days despite supportive care), or any drug-related grade 4-5 non-hematologic toxicity (excluding infection). The accrual will be halted if excessive numbers of unacceptable toxicities is equal to

or exceeds b_n out of n patients with full follow-up (see Table below). This is a Pocock-type stopping boundary that yields the probability of crossing the boundary at most 0.05 when the rate of unacceptable toxicity is equal to the acceptable rate of 0.2.

Number of Patients, n	1	2	3	4	5	6	7	8	9	10	11	12	13	14	15	16	17	18	19	20
Boundary, b_n	-	-	3	4	4	5	5	5	6	6	6	7	7	7	8	8	8	8	9	9
Number of Patients, n	21	22	23	24	25	26	27	28	29	30	31	32	33	34	35	36	37			
Boundary, b_n	9	10	10	10	11	11	11	11	12	12	12	13	13	13	13	14	14			

The stopping boundary above will guide enrollment as well as suspension of accrual (i.e., when to stop the trial if necessary). Initially 3 patients will be enrolled. Since the study is stopped when 3 unacceptable toxicities are observed in the first 3 patients, we will not enroll a new patient until at least one of the first 3 patients completes follow-up (i.e., reaches full hematologic recovery, deemed as refractory or CRi) and is confirmed not to have unacceptable toxicity. The enrollment will be continued in the same manner so that at any point in the trial the number of patients with unacceptable toxicities and the number of patients in the follow-up does not exceed b_n where n is the total number of patients accrued so far.

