4.9 Patient Replacement

If laboratory abnormalities exist on day 14 during induction, pembrolizumab administration can be delayed for 1 week, up to day 21, provided laboratory abnormalities correct themselves to levels defined in section 3.1 with supportive care. Patients who are ineligible for pembrolizumab administration by day 21 will be removed from the study and replaced by another subject.

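### Section 8.2's general accrual-pacing inequality does not enforce the logic of its own worked example: it is one patient too loose wherever the boundary steps up

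*Combined protocol and SAP*

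**What the plan says.** Section 8.2 (Continuous Monitoring for Toxicity) contains three linked rules.

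- **Halt.** "The accrual will be halted if excessive numbers of unacceptable toxicities is equal to" "or exceeds b_n out of n patients with full follow-up". Reaching the boundary is therefore enough to stop. The first half of the table reads "Boundary, b_n - - 3 4 4 5 5 5 6 6 6 7 7 7 8 8 8 8 9 9", so there is no boundary for n = 1 or 2, and b_3 = 3, b_4 = 4, b_5 = 4, b_6 = 5.
- **Worked example.** Three patients are enrolled first. "Since the study is stopped when 3 unacceptable toxicities are observed in the first 3 patients", the text continues, "we will not enroll a new patient until at least one of the first 3 patients completes follow-up" and is confirmed free of unacceptable toxicity.
- **General rule.** "The enrollment will be continued in the same manner so that at any point in the trial" patients with unacceptable toxicity together with the "number of patients in the follow-up does not exceed b_n where n is the total number of patients accrued so far".

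**The concern.** The example carries a clear principle: treat every patient still in follow-up as if toxic, and enrol nobody while that worst case would already reach the boundary. Because the halt is triggered by reaching b_n, the worst case must be strictly below the boundary before the next patient enters. The general rule instead allows the worst case to equal the boundary, and it takes the boundary at an n that already includes the new patient. After patient 4 no enrolment has an explicit bar of its own, so this inequality is the only numerical test a coordinator has. At stake is whether a patient starts treatment at a moment when, by the section's own reasoning, the trial might already have met its stopping criterion.

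**Working it through.** **Inputs (all from section 8.2).** The boundary is b_3 to b_37 = 3, 4, 4, 5, 5, 5, 6, 6, 6, 7, 7, 7, 8, 8, 8, 8, 9, 9, 9, 10, 10, 10, 11, 11, 11, 11, 12, 12, 12, 13, 13, 13, 13, 14, 14. The acceptable toxicity rate is 0.2, and the stated crossing probability is at most 0.05.

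**Step 1: reproduce the plan's figure.** An exact binomial recursion over n = 1 to 37, stopping when cumulative toxicities reach b_n, gives a crossing probability of 0.0497 at 20%. The stated 0.05 holds. At assumed rates of 30%, 40% and 50% the probability is 0.339, 0.776 and 0.972.

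**Step 2: compare the two pacing rules.** Call a patient cleared once follow-up ends without unacceptable toxicity, and consider enrolling patient m.

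- Example's logic: toxic + pending < b_(m-1) before enrolment, so cleared ≥ m − b_(m-1).
- General inequality as a standing limit: toxic + pending ≤ b_m after enrolment, so cleared ≥ m − b_m.

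The rules differ exactly where b_m = b_(m-1) + 1:

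| Patient m | b_(m-1) | b_m | Cleared needed, inequality | Cleared needed, example's logic |
|---|---|---|---|---|
| 4 | 3 | 4 | 0 | 1 |
| 6 | 4 | 5 | 1 | 2 |
| 9 | 5 | 6 | 3 | 4 |
| 12 | 6 | 7 | 5 | 6 |
| 15 | 7 | 8 | 7 | 8 |
| 19 | 8 | 9 | 10 | 11 |
| 22 | 9 | 10 | 12 | 13 |
| 25 | 10 | 11 | 14 | 15 |
| 29 | 11 | 12 | 17 | 18 |
| 32 | 12 | 13 | 19 | 20 |
| 36 | 13 | 14 | 22 | 23 |

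The gap is always one patient and does not accumulate. At the other 23 of the 34 enrolments (patients 4 to 37) the rules agree.

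*Example at patient 6.* Five patients are accrued, one is cleared and four are toxic or pending. If all four prove toxic, 4 ≥ b_5 = 4 and the trial halts. The example's logic holds (4 < 4 is false). The inequality admits (4 + 1 = 5 ≤ b_6 = 5).

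**Step 3: exact limit on extra patients at a stop.** Suppose the halt comes with d patients followed up, at least b_d toxicities and k ≥ 1 still pending, so the last patient enrolled was number d + k.

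- Example's logic requires b_d + k ≤ b_(d+k-1). The table rises by at most 1 per step, so b_(d+k-1) ≤ b_d + k − 1. This is impossible, so k = 0.
- The inequality requires b_d + k ≤ b_(d+k), so the table would have to rise at k consecutive steps. It never rises twice in a row, so k ≤ 1.

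**Step 4: average size, by simulation.** Assumptions: patient 4 is held until one is cleared, toxicity is counted at the end of follow-up, follow-up is uniform over 30 to 47 days, and nobody is replaced. There were 12,000 to 40,000 trials per setting. Mean extra patients per trial under the inequality (zero under the example's logic):

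| Candidate availability (assumed) | 20% toxicity | 40% toxicity (assumed) |
|---|---|---|
| Always one waiting | 0.027 | 0.414 |
| 14-day mean gap | 0.026 | 0.38 |
| 30-day mean gap | 0.020 | 0.29 |

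With a patient always waiting, trials that stop have 0.52 to 0.57 extra patients across rates of 20% to 50%. As a cross-check, stopping probability times mean at a stop gives 0.0497 × 0.56 ≈ 0.028 and 0.776 × 0.54 ≈ 0.42, in line with the first row. Follow-up of 25 to 77 days instead leaves the always-waiting figures at 0.027 and 0.414 per trial.

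**The case against.** The best defence is that the inequality is not a licence to enrol. The sentence says enrolment goes on in the manner of the example, and the limit is a result that must then hold. Anyone who follows the example's logic satisfies it automatically: if the count before enrolment is below b_(m-1), the count afterwards is at most b_(m-1), which is at most b_m. This part stands. The inequality is weaker than the example, not incompatible with it. A reader might infer that section 8.2 contradicts itself outright, or that it lets patient 4 in with nobody cleared. The documents do not support that, because both statements can be obeyed together and the preceding sentence bars patient 4 explicitly.

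A second defence is that n could mean the patients accrued before the candidate, with the candidate counted as in follow-up. Then 3 + 1 > b_3 = 3 means hold and 2 + 1 ≤ 3 means enrol, as in the example. That reading removes the gap, but the text does not state it, and a limit that applies at any point in the trial naturally includes everyone accrued.

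Oversight also helps in part. Section 7.4 provides continuous safety monitoring by the principal investigator and team meetings with biostatisticians. Section 9.4 requires central registration for affiliate sites, although the coordinating institution may register its own patients. None of this supplies the missing test.

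**Conclusion.** The concern holds in a limited form. Read as the standing limit it describes, the general inequality does not enforce the worked example's logic at 10 enrolments beyond the explicitly barred patient 4. The cap of one extra patient at a stop is exact and follows from the printed table. The averages, about 0.03 per trial at 20% and 0.3 to 0.4 at an assumed 40%, depend on assumed accrual and follow-up times.

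Two larger inferences should be resisted. First, the stopping rule is not compromised: the halt counts patients with completed follow-up, so pacing does not alter the table or the 0.0497. Second, at 20% toxicity the inequality admits at least one patient whom the example's logic would hold in 99% of simulated trials with a patient always waiting (64% with a 14-day gap, 27% with a 30-day gap). That counts early admissions, not patients left in follow-up after the boundary was reached.

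A side question is unquantified. Section 4.9 says "Patients who are ineligible for pembrolizumab administration by day 21 will be removed from the study and replaced by another subject", and section 8.2 does not say whether such patients stay in the accrued n. Sections 2.4.2 and 6.8 make receipt of pembrolizumab the condition for toxicity evaluation, which points to leaving them out of the toxicity count, but they do not settle the pacing n.

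**What to change.** Replace the last sentence of section 8.2 with:

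> After the first 3 patients, a new patient is enrolled only if, before that enrolment, the number of patients with unacceptable toxicity plus the number still in follow-up is less than b_n, where n is the number of patients already accrued (not counting the candidate).

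This reproduces the example (3 < 3 is false, so hold; after one clears, 2 < 3, so enrol), changes nothing at the 23 enrolments where the rules already agree, and leaves no pending patient at a stop.

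Simply changing the existing standing limit to strictly less than b_n would not work. It would bar the planned first three (3 < b_3 = 3 is false) and would be one patient stricter than the example at those 23 enrolments.

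Replaced patients are best left out of this sentence. If they are to be excluded from n, the text must also allow a patient replaced among the first three to be refilled up to three before the test applies, because b_1 and b_2 are undefined.

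The cost is one sentence and some waiting; the boundary table stays as it is. With a patient always waiting, completed trials last about 17 days longer at 20% toxicity (roughly 283 against 265 days, each rounded) and about 33 days longer at an assumed 40% (383 against 350). With a 14-day mean gap between candidates the delays are about 8 and 25 days.

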8.3 Data Analysis Plans

The primary endpoint of this study is the overall CR rate (CR+CRi) after HiDAC salvage followed by pembrolizumab on day 14. Responses will be assessed by standard international European LeukemiaNet Guidelines.²¹

Secondary endpoints include the following:

- Rates of unacceptable toxicity defined as any drug-related grade 3 non-hematologic toxicity (exceptions: fever, rash, infection, infusion reactions, nausea, fatigue and anorexia) lasting for >7days despite supportive care, or any drug-related grade ≥ 4 non-hematologic toxicity (excluding infection)
- Clinician assessed toxicity of HiDAC followed by pembrolizumab will be classified and graded according to NCI CTCAE, version 4.0.
- Objective overall response rates will be defined as PR+CR+CRi as determined by international European LeukemiaNet Guidelines in AML.²¹
- Clinician assessed toxicity of pembrolizumab maintenance will be classified and graded according to NCI CTCAE, version 4.0
- RFS will be defined as time from day 1 of CR/CRi to relapse or death from any cause.
- PFS will be defined as time from day 1 of response (i.e., PR/CR/CRi) to progression or death from any cause.
- OS will be defined as time from day 1 of treatment until date of last known follow up or death of any cause.

Survival distributions will be summarized using the method of Kaplan and Meier. We will report median time where possible. All demographic and analytic data will be summarized by descriptive statistics. Categorical data will be summarized using frequency tables while summary statistics such as means, medians, standard deviation, range, etc., will be provided for continuous data. 95% confidence intervals will be reported as well.

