1.0 BACKGROUND AND RATIONALE

1.1 Study Synopsis

This is an open-label, single arm, multicenter phase 2 study of standard salvage high dose cytarabine (HiDAC) on days 1 through 5 followed by a single dose of the humanized monoclonal antibody targeted against cell surface receptor programmed cell death-1 (PD-1), pembrolizumab, on day 14 as induction therapy in patients with relapsed and refractory acute myeloid leukemia (AML). Patients who achieve at least a partial response (PR) post-induction will continue on pembrolizumab every 3 weeks for up to 1 year of maintenance therapy. We plan to enroll 37 patients in a Simon's two-stage design.

The hypothesis of this study is that HiDAC followed by pembrolizumab will be effective in relapsed and refractory AML with a combined complete remission (CR)/CR with incomplete recovery (CRi) rate of $\geq 40\%$, superior to a historical control of 20%. We also hypothesize that the rate of unacceptable toxicity associated with HiDAC followed by pembrolizumab will not significantly exceed 20% (see section 2.4.2). Secondary endpoints include toxicity of this combination when used as induction, overall objective response rate (CR+CRi +PR) post-induction, toxicity of pembrolizumab maintenance in those patients with a response after induction, and progression-free survival (PFS), relapse-free survival (RFS) and overall survival (OS) in patients who receive maintenance pembrolizumab. We will also explore for an association between potential immune biomarkers and clinical outcomes with pembrolizumab. The overarching goals of these correlative studies are: 1) to identify and characterize mechanisms involved in T cell dysfunction in AML, 2) to identify potential predictive biomarker candidates to allow better selection of AML patients who may benefit from pembrolizumab, and 3) to identify new pathways that could be targeted to enhance the efficacy of pembrolizumab in AML.

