2.0 STUDY OBJECTIVES

2.1 Primary Objective

Estimate the objective overall rate of CR (CR+CRi) for age-adjusted HiDAC (age <60 years: 2 gm/m² IV Q12hours days 1-5; age ≥60 years: 1.5 gm/m² IV Q12hours days 1-5) followed by pembrolizumab 200 mg IV on day 14 in relapsed and refractory AML patients

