8.0 STATISTICAL CONSIDERATIONS

8.1 Study Design and Sample Size

This is a multi-center prospective open-label single arm phase 2 study assessing the activity of age-adjusted HiDAC (<60 years: 2 gm/m² IV Q12hours days 1-5; ≥60 years: 1.5 gm/m² IV Q12hours days 1-5) salvage induction treatment followed by pembrolizumab 200 mg IV on day 14 for relapsed or refractory AML patients.

The subjects who achieve a response (CR, CRi, or PR) to induction phase HiDAC followed by pembrolizumab 200 mg IV on day 14, as assessed by standard international European LeukemiaNet Guidelines in AML,²¹ will receive pembrolizumab 200 mg IV Q3weeks of maintenance therapy beginning 10-30 days following full hematologic recovery from induction phase. Maintenance treatment will continue until disease progression, toxicity, physician and/or patient discretion, or up to 1 year of treatment.

Simon's like two-stage design with relaxed stopping for futility will be used.⁵³ The null hypothesis that the true CR rate (CR/CRi) for HiDAC followed by pembrolizumab is 20% will be tested against a one-sided alternative hypothesis. In this study, "relaxed stopping" refers to inclusion of PR in the first stage as some of these PRs may convert to a CR during maintenance. In the first stage, 19 patients will be enrolled. If the number of patients who achieve a CR/CRi plus the number of patients with PR is equal to 4 or fewer in these 19 patients, the study will be stopped. Otherwise, 18 additional patients will be enrolled for a total of 37 patients. The null hypothesis will be rejected if 12 or more CR/CRi's are observed in 37 patients.. Assuming that the PR rate has a uniform distribution, Uniform (0, 0.05), under H₀, this design yields a type 1 error rate of at most 5% and power of at least 84% when the true CR rate for HiDAC followed by pembrolizumab is 0.4.

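### Does the analysis plan need to name the method for the 95% interval on the CR/CRi rate?

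*Combined protocol and SAP*

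**What the plan says.** Section 2.1 sets the primary objective as estimation: "Estimate the objective overall rate of CR (CR+CRi"). Section 8.3 repeats the endpoint ("The primary endpoint of this study is the overall CR rate (CR+CRi) after HiDAC salvage followed by pembrolizumab on day 14") and names Kaplan-Meier for the survival endpoints. It closes with one general sentence after the descriptive statistics: "95% confidence intervals will be reported as well". Nothing else in the document describes an interval for a proportion.

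The decision is specified separately and in full in Section 8.1. The null rate of 20% "will be tested against a one-sided alternative hypothesis". If the stage 1 total of CR/CRi plus PR "is equal to 4 or fewer in these 19 patients, the study will be stopped"; otherwise 18 more patients are enrolled, making 37. "The null hypothesis will be rejected if 12 or more" CR/CRi are seen among the 37. The section claims a type I error of at most 5% and power of at least 84% at a true rate of 40%, with the PR rate taken as uniform between 0 and 5%. The Synopsis (Section 1.1) states the hypothesis as a rate of at least 40%, "superior to a historical control of 20" per cent.

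**The concern.** For an objective framed as estimation, the interval is part of the primary result, and the plan leaves its construction open. That matters more than usual here for three reasons.

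- The sample is small, so standard binomial intervals differ in coverage and in their limits. The futility stop adds a second possible denominator of 19.
- A Wald interval would comply with the text. After a stage 1 stop with no CR/CRi it has zero width, and with 1 to 3 of 19 its lower limit is negative.
- The test is one-sided at about 5%, whereas a 95% interval is normally read as two-sided. A trial that succeeds at 12 of 37 would therefore be reported beside an interval containing the historical 20%, with no planned explanation.

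At stake would be whether the published interval has roughly its stated coverage, and whether its method could be picked after the result was known.

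**Working it through.** **Inputs (Section 8.1).** Stage 1 has 19 patients; stop if CR/CRi + PR ≤ 4. Stage 2 has 18 patients; reject at CR/CRi ≥ 12 of 37. Null rate 20%, alternative 40%, PR rate r between 0 and 5%.

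**Model.** Stage 1 counts (CR/CRi, PR, neither) are multinomial with n = 19 and probabilities (p, r, 1 − p − r). If stage 1 continues, a Binomial(18, p) count of CR/CRi is added. The interval uses n = 19 after a stop and n = 37 otherwise. Coverage at p is the total probability of outcomes whose interval contains p.

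**Step 1: the plan's own figures.** At r = 0, 2.5% and 5%, type I error is 4.71%, 4.85% and 4.96%, and power is 84.1%, 85.1% and 85.8%. Both claims in Section 8.1 hold, and neither depends on the interval.

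**Step 2: coverage of nominal two-sided 95% intervals,** p from 20% to 40%, over the three PR rates:

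| Interval | Mean coverage | Minimum |
|---|---|---|
| Exact (Clopper-Pearson) | 96.8–97.0% | about 95.4% |
| Wilson | about 95% | about 92.2% |
| Wald | 91.1–91.4% | about 85.0% |

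Other standard choices lie between: Jeffreys averages about 94.4% and Agresti-Coull about 95.6%. Without Wald, the spread is about 94% to 97%. With a fixed n of 37, Wald already averages only 93.3% with a minimum of 89.7%, so the binomial method drives much of the shortfall and the early stop adds to it.

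**Step 3: limits at the decision boundary.** For 12/37 the proportion is 0.3243.

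- Wald: 0.3243 ± 1.96 × √(0.3243 × 0.6757 / 37) = 0.3243 ± 0.1508, that is 17.3% to 47.5%.
- Wilson: 19.6% to 48.5%. Exact: 18.0% to 49.8%. Jeffreys lower limit: 19.1%.
- One-sided exact lower bound: 19.9%.

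All of these include 20%. For 13/37 the lower limits are Wald 19.75%, exact 20.2%, Jeffreys 21.3% and Wilson 21.8%, so only Wald includes 20%. For 11/37, a failure, the lower limits run from 15.0% to 17.7%, so no method makes a failed trial look like a success.

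**Step 4: why 12/37 behaves this way.** An exact two-sided 95% interval excludes 20% on the low side only if P(X ≥ x) at p = 20% is at most 2.5%. For a fixed n of 37, P(X ≥ 12) = 5.17%, which is above 2.5%, and P(X ≥ 13) = 2.31%, which is below it. The count rule works at 5%, and the futility stop brings 5.17% down to 4.71–4.96%. So 12/37 falls between the two levels whichever interval is named.

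**Step 5: how often this arises.** The probability of finishing at exactly 12/37 is 2.5–2.7% at a true rate of 20%, 11.6–12.5% at 30% and 7.8–8.5% at 40%. For 13/37, the one successful count where Wald and the other methods disagree, it is 1.3%, 10.2–10.6% and 10.6–11.1%.

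**Step 6: early stop.** At a true rate of 20%, a stage 1 stop with 0 to 3 CR/CRi has probability 38–46%. Wald limits are then 0 to 0 at 0/19, −4.8% to 15.3% at 1/19, −3.3% to 24.3% at 2/19 and −0.6% to 32.2% at 3/19. The exact interval gives 0 to 17.6% at 0/19 and 3.4% to 39.6% at 3/19.

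**The case for a change.** The best case for a change is that methods which all fit the sentence differ materially for the primary result, that one of them can cover as little as 85%, and that two sentences would close the gap at no cost to design or data. If an exact interval is what the trial statistician intends, writing it down costs nothing. At 13/37 the method also determines whether the interval excludes the historical rate, and the trial is open-label, so the choice could follow the result.

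The textual gap stands: no method is named and no redaction explains its absence. The consequences are weaker than they look. The 91% figure and the impossible limits need an analyst to choose Wald, which the document never mentions and whose failure with small counts is well known. A result-driven choice also has little to work with. At 13/37 a team wanting 20% excluded would be led to the exact or Wilson interval, which are the better ones; at 12/37 no common method excludes it; at 11/37 or fewer none turns a failure into an apparent success. The mismatch at 12/37 would remain after a method was named and is explained by one sentence in the report.

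Fixing the text in advance has its own difficulty. Prescribing 37 or 19 as the denominator would omit a halt for toxicity under Section 8.2, which can occur at other sample sizes.

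**Conclusion.** No change to the plan follows. Section 8.3 omits a detail; it does not state a wrong rule. The decision, the type I error (4.7–5.0%) and the power (84.1–85.8%) rest on the count rule in Section 8.1 and are untouched. The intervals an experienced statistician would reach for, exact or Wilson, average about 95% to 97% over true rates of 20% to 40%. An interval that includes 20% at 12/37 is what a one-sided 5% rule beside a two-sided 95% interval produces.

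This rests on some assumptions. The 20–40% range is chosen to match the null and alternative; outside it the exact interval can dip slightly below its level (94.2% at a true rate of 47% with no PRs). The enumeration does not model a toxicity halt under Section 8.2, or PRs that become CRs during maintenance, which Section 6.9 counts as overall CRs. It also assumes that the analyst does not use a Wald interval. If one were reported, the criticism would belong to the report, and it could be recomputed from the count and denominator.
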